The hypothesis of this exploratory clinical trial in patients with prostate cancer metastatic to bone is that [18F]Fluciclovine-PET/CT uptake will correlate with the type of bone metastasis present (blastic, lytic, marrow, mixed) as has been seen in pre-clinical animal models. It is expected that lytic and marrow foci will exhibit the greatest [18F]Fluciclovine-PET/CT uptake.

The primary exploratory objectives of the study are:

- Abnormal [18F]Fluciclovine uptake on visual assessment will differ by the type of metastatic lesion present (blastic, lytic, marrow, mixed).
- SUVmax and SUVmean on [18F]Fluciclovine-PET/CT imaging will differ by the type of metastatic lesion present (blastic, lytic, marrow, mixed).

Secondary Exploratory Objectives are outlined below

- Determine if a 25% or greater reduction in aveSUVmax or aveSUVmean on [18F]Fluciclovine-PET/CT imaging after completion of all radiation therapy will be predictive of increased time to biochemical failure.
- Determine the correlation between the number of lesions, their visual uptake, and semi-quantitative uptake on 99mTc-MDP bone scintigraphy and [18F]Fluciclovine- PET/CT at baseline
- Determine the correlation between the number of lesions, their visual uptake, and semi-quantitative uptake on 99mTc-MDP bone scintigraphy and [18F]Fluciclovine- PET/CT after 3 and 6 cycles of treatment.

Study Population

Age of Participants: 18+

Sample Size:

At Utah: 15
All Centers: 18

Inclusion Criteria:

- Enrollment on IRB #102312 (A Phase 2 Study of Radium-223 and Radiotherapy in Hormone-Naïve Men with Oligometastatic Prostate Cancer to Bone).
- Patients must document their willingness to be followed for up to 24 months after recruitment by signing informed consent documenting their agreement to allow access to the data obtained on IRB #102312 and information and data entered into a research database.
- All patients, or their legal guardians, must sign a written informed consent and HIPAA authorization in accordance with institutional guidelines.

Exclusion Criteria:

- Patients with known allergic or hypersensitivity reactions to previously administered radiopharmaceuticals. Patients with significant drug or other allergies or autoimmune diseases may be enrolled at the Investigator's discretion.

- Patients who require monitored anesthesia for PET scanning.
- Patients who are too claustrophobic to undergo PET scanning.

Design

Prospective Biomedical Intervention or Experiment
Open Label Trial

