We focus on separate comparisons of the difference in SUV_{max} and SUV_{mean} in osteolytic vs osteoblastic lesions. Both SUV_{max} and SUV_{mean} are expected to be appreciably higher in osteolytic lesions. The data available for assessment of power is sparse. Oka reported tumor to background (T/BG) ratios of approximately 3 ± 1.0 and 4.5 ± 1.0 (mean \pm SD) for ^{14}C -fluciclovine uptake in osteoblastic and osteolytic lesions respectively in bone metastasis models in mice (Oka et al. 2017). A recent human study by Janssen provides some information that can be used in the current study to determine the sample size (Janssen et al 2017). The study assessed $[^{68}Ga]PSMA-HBED-CC$ uptake in osteolytic, osteoblastic, and bone marrow metastases in prostate cancer patients. It is expected that the $[^{68}Ga]PSMA-HBED-CC$ and $[^{18}F]Fluciclovine$ will behave similarly for the detection of bone metastases depending on the type (blastic, lytic, marrow, mixed). As reported in table 3 of that manuscript, a median SUV_{max} for $[^{68}Ga]PSMA-HBED-CC$ imaging of 10.6 ± 7.1 and 24.0 ± 19.3 in osteoblastic and osteolytic bone metastases in prostate cancer patients with at least one bone metastasis (Janssen et al 2017, The number of osteolytic and osteoblastic lesions in the study were 21/154 (13.6%) and 80/154 (51.9%) respectively, and there were approximately 5 lesions per subject (154 lesions in 30 patients).

Guided by the data in Janssen (Janssen et al., 2017) we assume:

1. 5 lesions per subject. As in Janssen (Janssen et al., 2017) uptake of lesions in the same patient is assumed to be independent.
2. A standard deviation of 14.5 for mean SUV_{max} or SUV_{mean} .
3. The proportion of osteoblastic and osteolytic lesions will be 50% and 13% respectively.
4. The use of separate two sample t - tests at the one sided 0.05 significance level for comparison of SUV_{max} and SUV_{mean} between osteoblastic and osteolytic lesions.

With these assumptions a sample size of 18 evaluable subjects will provide 80% power to detect a difference of 14.7 in mean SUV_{max} or SUV_{mean} between osteolytic and osteoblastic lesions.

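### The claimed 80% power for a difference of 14.7 does not follow from the listed assumptions, which give about 12.0 at 80% power, or 92% power at 14.7

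*Combined protocol and SAP*

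**What the plan says.** The Justification of Sample Size gives every input needed to repeat the calculation:

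- Lesions: "5 lesions per subject", with no clustering, because "uptake of lesions in the same patient is assumed to be independent".
- Spread: "A standard deviation of 14.5 for mean" SUVmax or SUVmean, one common value.
- Split: "The proportion of osteoblastic and osteolytic lesions will be 50% and 13% respectively".
- Test: separate two-sample t-tests "at the one sided 0.05 significance level for comparison of" SUVmax and SUVmean.

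The conclusion is: "With these assumptions a sample size of 18 evaluable subjects will provide 80% power to detect a difference of 14.7 in mean" (either SUV measure, with the two lesion types compared). The planned total under Study Population is "All Centers: 18". The section mentions no design effect, attrition allowance, multiplicity adjustment or unequal-variance adjustment.

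**The concern.** The concluding sentence presents 14.7 as the consequence of the list above it, but the list gives a clearly smaller detectable difference. This is the only sample-size justification in the plan. It supports both the total of 18 and the primary t-test comparison.

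Two things are at stake:

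- **Comparison with the planning data.** The human values that guide the plan differ by 24.0 − 10.6 = 13.4. If 14.7 really were the 80% point, the design would fall short of 80% power at 13.4. Under the listed assumptions it exceeds 80%.
- **Which assumption is in force.** If 14.7 came from another sample size, alpha, sidedness, standard deviation or lesion count, then a listed assumption is wrong rather than the result. The Data Analysis section gives neither alpha nor sidedness for the primary t-tests, so the sample-size section is the only place where they are stated.

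**Working it through.** **Inputs** (Justification of Sample Size): 18 subjects; 5 independent lesions each; 50% osteoblastic and 13% osteolytic; SD 14.5; one-sided alpha 0.05; power 80%.

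**Step 1, lesion counts.** 18 × 5 = 90 lesions. Osteoblastic: 0.50 × 90 = 45. Osteolytic: 0.13 × 90 = 11.7.

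**Step 2, standard error.** SE = SD × √(1/n₁ + 1/n₂) = 14.5 × √(1/45 + 1/11.7) = 4.758, with 45 + 11.7 − 2 = 54.7 degrees of freedom.

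**Step 3, attempt to reproduce the plan's figure.** Normal approximation: (1.645 + 0.842) × 4.758 = 11.83. Exact solution with the noncentral t distribution: 11.98, or 11.98/14.5 = 0.83 SD. The plan's 14.7 is not reproduced; 14.7/11.98 = 1.23, so it is 23% larger.

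**Step 4, power at the stated difference and at the planning gap.**

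| Osteolytic lesions (vs 45 osteoblastic) | Detectable difference at 80% power | Power at 14.7 |
|---|---|---|
| 11 | 12.28 | 90.8% |
| 11.7 | 11.98 | 92.0% |
| 12 | 11.86 | 92.5% |

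Power at 13.4 with 45 and 11.7 lesions is 87.2%. If 14.7 were the true 80% point, power at 13.4 would be about 73%.

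**Step 5, what would give about 14.7.** Each route below departs from something the plan states. All use SD 14.5 unless noted.

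| Departure | Detectable difference at 80% power |
|---|---|
| 18 subjects, two-sided 0.05 | 13.57 (power 85.9% at 14.7), so not sufficient |
| 12 subjects, one-sided 0.05 | 14.77 (30 vs 7.8 lesions); 14.62 (30 vs 8) |
| 15 subjects, two-sided 0.05 | 14.92 (37.5 vs 9.75); 14.75 (38 vs 10) |
| 18 subjects, two-sided 0.025, normal approximation | 14.67 |
| 18 subjects, one-sided 0.05, group SDs 7.1 and 19.3, normal approximation | 14.71 (11 osteolytic); 14.27 (11.7); 14.10 (12) |
| 18 subjects, two-sided 0.05, Welch test, 11 osteolytic lesions | 14.60 |
| 18 subjects, one-sided 0.05, 3.3 to 3.5 lesions per subject | 14.85 to 14.40 |
| 18 subjects, one-sided 0.05, within-patient correlation 0.125 | 14.67 |

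Several incompatible designs land near 14.7, so the documents cannot show which was used, if any.

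**The case against.** The strongest case on the other side accepts the arithmetic and disputes its weight and the remedy.

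- **The error is conservative and the study exploratory.** The listed assumptions give more power than claimed, no procedure changes, and the plan itself calls the data for assessing power sparse. This stands. It limits the consequences but does not make the sentence correct.
- **The standard deviation may be the source.** The group SDs printed in the same section (7.1 and 19.3) give 14.71 with sample size, alpha and sidedness left as stated. This is a fair addition to the candidates. The match needs the osteolytic count cut to 11, and it replaces the common 14.5, which is about the root mean square of those two SDs: √((7.1² + 19.3²)/2) = 14.54. It remains unproven.
- **Printing 12.0 or 92% could look too favourable.** Purpose and Objectives limits patients to at most 5 bone lesions, so 5 per subject may be a ceiling: 4 per subject gives 13.44 and 3 gives 15.61. A one-sided Welch test with the two group SDs gives 75% to 79% power at 14.7 and 68% to 72% at 13.4 (11 to 12 osteolytic lesions). These are good reasons to re-examine the assumptions. They do not make 14.7 follow from the assumptions as printed.
- **The 13.4 benchmark is imperfect.** The plan labels the values behind it as medians, while 14.7 is a difference in means. This stands, so the comparison is indicative only.

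**Conclusion.** The concern holds. Under the plan's own list, 18 evaluable subjects give 80% power for a difference of about 12.0, and 92% power for 14.7. The stated difference is 23% too large, or equivalently the stated power is 12 percentage points too low. Rounding the osteolytic count moves the detectable difference only between 11.86 and 12.28, and a two-sided 0.05 test does not close the gap.

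These results take the listed assumptions as given: independent lesions, exactly 5 per subject, a common SD of 14.5 for both SUV measures, and the 50%/13% split. They do not endorse those assumptions. The origin of 14.7 cannot be settled from the documents, and the error alone does not show that more patients are needed.

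**What to change.** First establish how 14.7 was obtained. Then do one of the following:

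1. If the listed assumptions are the intended ones, state that 18 evaluable subjects give 80% power for a difference of about 12.0, or that power at 14.7 is 92%.
2. If a different input was used (number of subjects, alpha, sidedness, standard deviation, lesions per subject or within-patient correlation), correct that item in the list and recompute, so that list and result agree.

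When the sentence is revised, it would help to say that the SD of 14.5 rests on SUVmax data for another tracer, because the plan cites no human data for SUVmean. Quoting the result also in SD units (0.83 SD under option 1) is optional.

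The cost is one or two corrected sentences. Option 1 changes neither enrolment nor procedures. Under option 2, the adequacy of 18 subjects should be judged on the recomputed figure.
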